1.2 Secondary Objectives

The secondary objectives are to examine the effects of cigarette filter ventilation on subjective measures such as cigarette dependence and responses to study cigarettes. As an exploratory analysis, the concordance for toxicant levels analyzed across multiple biosamples (urine, saliva, blood spots and hair) and subject acceptability of collecting these samples at home will be determined.

We hypothesize that unventilated filter cigarettes will be associated with no higher number of cigarettes smoked, biomarkers of exposure or cigarette dependence and satisfaction compared to ventilated filter cigarettes; but smokers assigned to the ventilated filter cigarettes will smoke cigarettes more intensely and perceive them as less harmful than smokers assigned to the unventilated cigarettes. We also hypothesize the level of toxicant exposure will be concordant across various methods of collecting biological samples.

2 Background

The Changing Cigarette. Over 34 million people in the United States,¹ and about 1.2 billion globally,² smoke cigarettes. With about 500,000 deaths per year in the US^{1,3} and 6 million per year worldwide,² it is critical to have strong tobacco control policies in place to minimize the casualties from tobacco use.

The Family Smoking Prevention and Tobacco Control Act (FSPTCA), signed into legislation in 2009, provides the FDA with the authority to regulate tobacco products. One of the provisions in this legislative act empowers the FDA to assert product standards that would reduce harmful constituents in tobacco products, including alterations in the design of the product. A product standard that requires consideration is the use of ventilation in cigarette filters. Filter ventilation came onto the marketplace in the 1960s in response to consumer concerns about the negative health impact of cigarettes after a series of reports, including the 1964 U.S. Surgeon General's Report⁴ (SGR), linked smoking to lung cancer and other diseases. Filter ventilation was a way for the tobacco industry to reduce machine-determined tar and nicotine yields in cigarettes, providing consumers with the perception that these cigarettes were "safer" to smoke. This perception, however, was false because

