Developing the science to determine if filter ventilation should be banned. The 2014 SGR stated that, "if the risk of lung cancer has increased with changes in the design and composition of the cigarettes, then the potential exists to reverse the risk through changes in design and composition (p. 186)." The report went on to say that "even a modest reduction in the large burden of mortality from lung cancer would result in saving a substantial number of lives over time (p. 186)." This study will use a systematic and comprehensive effort to examine one type of design feature, based on extensive review of the literature that may have led to the increase in lung cancer deaths, in particular adenocarcinoma lung cancer. Independent of the effects of ventilated cigarettes on lung adenocarcinoma, removing filter ventilation has the potential to reduce misperceptions regarding the relative harm of these cigarettes. We begin with the premise that ventilated cigarettes should be regulated, and herein we study its complete removal. This proposed study complements other studies conducted by our research team examining the effects of cigarette ventilation levels on biomarkers from lung bronchoscopies and particle distribution in the lungs. The aim of this study will be to examine the impact of ventilated vs. unventilated cigarettes on several biomarkers of specific exposures and effects (assessed via urine, saliva, oral cells and potentially hair and blood and inhalation measures), and examining smoking topography via spent filter analysis while holding levels of TSNAs constant. The overarching goal is to make sure that a proposal to ban filter ventilation does not lead to greater toxicant exposure, dependence and thereby potential harm, complementing other program project studies that examine misperceptions of ventilated cigarettes and potentially greater harm by examining the effects of these cigarettes in the lung.

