10.1 Trial Endpoints

Primary Endpoint:

- The change in total NNAL from visit 00 to week 6 visit.
- The mean CPD based on 7-day IVR data between week 00 and Week 6 visit

Secondary Endpoint:

- Change in TNE, CEMA, and PheT from visit 00 to week 6 visit
- Change in intensity of smoking measured by filter analysis collected at 00, Week 3 and Week 6.
- Change in parameters of inhalation depth measured at 00 and Week 6.
- Change in subjective measures (dependence as measured by the FTND, mCES, and Perceived Health Risk) from visit 00 to Week 6 visit.

Exploratory Endpoints:

- Change in biomarkers of other volatile organic compounds (e.g.,3-HPMA, HMPMA) from visit 00 to Week 6 visit.
- Determine concordance in biomarkers of exposure across different sample collection methods.

Secondary Endpoint

Safety Endpoints:

- Adverse Events (AEs)

- Serious adverse events (SAEs)

Randomization

Subjects will be randomly assigned using a stratified (by site), block randomization scheme into the following groups: (1) ventilated filter cigarettes; or (2) unventilated filter cigarettes.

Sample size and power considerations

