To determine the sample size for a test of non-inferiority for unventilated filter cigarettes compared to ventilated filter cigarettes (control group), we used pilot data from our original ventilated/unventilated study 1 ([name], personal communication). For the purposes of sample size considerations, we will focus on total NNAL as one of the primary outcomes. Seventy subjects had a baseline NNAL value while smoking their usual brand and 19 and 16 subjects had an end of study NNAL value for the ventilated and unventilated groups, respectively. The endpoint of interest is the change in NNAL from baseline. To normalize the distribution of NNAL, the calculations were performed in the log scale. The non-inferiority margin (NIM) was set at a 15% change between groups. This criterion was chosen because it is close to, but not greater than the upper limit of the 95% confidence interval (CI) for the geometric mean of the change in NNAL. Therefore, 73 subjects per group will achieve 80% power to detect non-inferiority for the mean change in NNAL using a one-sided, two sample t-test with a significance level of 0.05. Furthermore, with these sample sizes, a one-sided, two-sample t-test for the mean difference in cigarettes per day (CPD) from baseline will have 90% power to determine non-inferiority with a significance level of 0.05 if the NIM is 2 cigarettes. A mean difference between ventilation groups of less than 2 cigarettes is considered to be in the range of equivalence. To accommodate a 10% loss-to-follow-up rate, we plan to enroll 81 subjects per group for a total of 162.

Study Populations

Intent-to-treat

The first analysis of all primary and secondary endpoints will adhere to the intent-to-treat principle. Under this principle, all subjects randomized to one of the two study arms will be included in the analysis in the group to which they were randomized regardless of protocol violations and compliance to treatment assignment.

Per-Protocol

A second per-protocol analysis will include only participants who complete the 6 week visit without protocol violations or non-compliance.

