The secondary analyses include the other biomarkers (as listed above). The analysis for these potential toxicants will be the same as that outlined above for NNAL with measurements at end of Phase 2 (visit 00) and at the 6 week visit. A non-inferiority margin has not been established for many of these biochemical measures. Instead, group differences or ratios (if in the log scale) will be estimated with their 95% CI and examined as to whether or not they contain 0 for differences or 1 for ratios. Inhalation measures and smoking intensity (solanesol levels in the filter butts) will be analyzed with similar methods as the change in biomarker and CPD with regression models incorporating-covariates for baseline variables that may be different between groups ($p\text{-value}<0.2$). The FTND as a measure of dependency is a composite score that ranges from 0 to 10. With the expectation of non-inferiority for the unventilated group, a linear regression model for FTND at 6 weeks will include the FTND at baseline (visit 00) and the ventilation group indicator, plus any other important subject characteristic. The 95% CI for the estimated coefficient for the group indicator will be calculated to verify that it contains the value zero, indicating no difference in dependency between ventilation groups. The mCES and PHR questionnaires produce a series of subscales. To identify differences between ventilated and unventilated groups, non-parametric methods will be utilized, first with the Wilcoxon signed rank test to check for changes from end of Phase 2 to 6 weeks within each ventilation group and then with the Wilcoxon rank sum test for differences between groups.

Exploratory Analysis

The exploratory analysis for the other volatile organic biomarkers (listed in section 6.2) will be the same as that outlined above for NNAL and the other secondary biomarkers.

Correlation procedures (Pearson and Spearman) will measure the degree of association for the same biomarkers assayed from two or more biosamples.

Safety Endpoints

AEs and SAEs will be recorded as described in the Adverse Event SOP. AEs and SAEs will be tabulated separately for the two groups. We expect study product-related AEs and SAEs to be rare in this trial and, therefore, no formal statistical comparison of the rate of AEs and SAEs across treatment groups is planned for this trial.

Missing Data

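### FTND: a 95% CI that contains zero is read as no difference in dependence, and no FTND margin is given

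*Combined protocol and SAP*

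**What the plan says.** Section 10.1 lists the dependence endpoint among the secondary endpoints: "Change in subjective measures (dependence as measured by the FTND, mCES, and Perceived Health Risk) from visit 00 to Week 6 visit". Section 10.2 (Secondary Endpoint Analysis) introduces the scale, "The FTND as a measure of dependency is a composite score that ranges from 0 to 10", and the aim, "With the expectation of non-inferiority for the unventilated group". It specifies a linear regression of week-6 FTND on visit-00 FTND and group, plus other important characteristics. The 95% CI for the group coefficient "will be calculated to verify that it contains the value zero, indicating no difference in dependency between ventilation groups".

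Three other places bear on this:

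- Section 1.2 hypothesises that unventilated cigarettes are associated with "no higher number of cigarettes smoked, biomarkers of exposure or cigarette dependence and satisfaction" than ventilated ones.
- Section 2 (Background) gives the overarching goal as to "make sure that a proposal to ban filter ventilation does not lead to greater toxicant exposure, dependence and thereby potential harm".
- The sample size text in Section 10.1 sets margins for the two primary endpoints only: 15% for NNAL and 2 cigarettes for cigarettes per day (CPD). For CPD it adds: "A mean difference between ventilation groups of less than 2 cigarettes is considered to be in the range of equivalence".

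**The concern.** The FTND sentence is a decision rule with its conclusion attached, and the conclusion does not follow. A 95% CI contains zero when the two-sided test at 0.05 is not significant. That can happen because the groups are alike or because the data are too imprecise to separate them. Non-inferiority needs the upper limit for unventilated minus ventilated to lie below a stated margin, and FTND has none.

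The rule also favours imprecision: the wider the interval, the easier it is to pass. In the other direction, a CI wholly below zero (lower dependence with unventilated cigarettes) would fail the check, although it agrees with the hypothesis in Section 1.2. The plan does not say how such a result would be read.

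At stake is one of the study's stated aims. Section 8 says the results may help the FDA decide how to regulate tobacco products, so an unsupported statement that dependence does not differ would matter outside the trial.

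**Working it through.** **Is there a margin or rule elsewhere?** I set the candidate passages side by side.

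- Sample size text and primary analysis (Sections 10.1 and 10.2): margins for NNAL and CPD, none for FTND.
- Secondary Endpoint Analysis: "A non-inferiority margin has not been established for many of these biochemical measures". This covers biochemical measures. FTND is a questionnaire score.
- End of the Secondary Analysis text (Section 10.2): regression and repeated-measures models can be adapted for non-inferiority. No margin is given and FTND is not named.

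So the contains-zero check is the only FTND rule. The plan states no FTND power, SD or margin, so there is no FTND figure to reproduce.

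**Inputs.** From the documents: 73 evaluable per arm, 81 enrolled per arm, a two-sided 95% CI, and one-sided 0.05 for the primary tests. Assumed: residual FTND SD of 1.0, 1.5 or 2.0 points, with 2.5 as a wider case, and true increases of 0.25 to 1.0 point.

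**Formulas.** SE = SD × √(2/n), with √(2/73) = 0.1655. Half-width h = t(0.975) × SE, with t = 1.977 on 2n − 3 = 143 df (baseline-adjusted model). For a true increase δ,

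P(CI contains 0) = F(t) − F(−t),

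where F is the noncentral t distribution function with noncentrality δ/SE.

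**Chance that the CI contains zero, 73 per arm**

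| True increase (points) | SD 1.0 | SD 1.5 | SD 2.0 | SD 2.5 |
|---|---|---|---|---|
| 0.25 | 68% | 83% | 88% | 91% |
| 0.5 | 15% | 48% | 68% | 78% |
| 0.75 | 1% | 15% | 39% | 56% |
| 1.0 | 0% | 2% | 15% | 33% |

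Worked case, SD 2.0 and δ = 0.5: SE = 2.0 × 0.1655 = 0.331, noncentrality 0.5/0.331 = 1.51, probability 0.677. A simulation of 40,000 trials gave 0.676.

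**How far can a passing CI reach?** If the lower limit just touches zero, the estimate equals h and the upper limit equals 2h. With h = 0.327, 0.491, 0.654 and 0.818, the upper limits are 0.65, 0.98, 1.31 and 1.64 points.

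**Effect of sample size.** With all 81 per arm evaluable, the 0.5-point row becomes 11%, 44% and 65% for SD 1.0, 1.5 and 2.0. Planned attrition therefore moves these figures by only 3 to 4 percentage points. A larger loss shows the perverse incentive: at SD 2.0 and a true 1-point increase, 36 per arm instead of 73 raises the chance of a no-difference reading from 15% to 45%.

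**The case against.** The best counter-argument concerns weight. FTND is secondary and plays no part in the sample size. The adjusted estimate and its CI are calculated whatever label is attached, so a careful reader can judge the difference. The primary tests use margins and are untouched. All of this stands and limits the consequence, but it does not make the prespecified conclusion valid.

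A charitable reader could apply the remark that regression models can be adapted for non-inferiority, since the FTND model is a linear regression and the remark comes just before it. However, the remark is permissive and supplies no margin, and the FTND paragraph then sets a different rule.

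The probabilities rest on assumed SDs, and no FTND difference that matters is defined. Missing a 0.25-point increase may be of no consequence, so that row should not be read as an error rate. The reassurance about 1-point increases also depends on the SD: 15% at 2.0 becomes 33% at 2.5. Both points stand. The logical fault needs no assumed SD.

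The point about a CI wholly below zero is mainly loose drafting, since the stated expectation makes a favourable reading natural.

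**Conclusion.** The concern holds. Followed as written, the plan would treat failure to detect a difference in FTND as evidence that there is none. The chance of doing so wrongly is uncontrolled, because it depends on the FTND variability and the true increase, and the documents give neither.

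For assumed SDs of 1.0 to 2.0 and 73 per arm, the rule often passes small to moderate increases, and it rarely passes a 1-point increase unless the SD is near 2 or above. It should be fixed because dependence is part of the stated hypothesis and goal. It does not threaten the primary NNAL or CPD conclusions.

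**What to change.** In Section 10.2, delete the clause that has the CI checked for zero and the conclusion drawn from it. Replace it with: *The adjusted group difference in FTND (unventilated minus ventilated) will be reported with its 95% CI; a CI containing zero is not evidence of no difference.* This removes the wrong inference. It leaves the Section 1.2 hypothesis on dependence without a formal decision rule, which is acceptable if FTND is to be reported by estimation. The opening phrase on expected non-inferiority should then be read as an expectation only.

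If a non-inferiority conclusion on FTND is wanted, also fix and justify a margin and confidence level before outcome data are analysed. Conclude non-inferiority only if the upper limit lies below the margin, and otherwise report the result as inconclusive.

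**Cost.** The replacement is text only: no change to data, visits or sample size. Some results now labelled no difference would become inconclusive. The optional margin needs a rationale that the documents do not contain, and its power depends on the choice. At 73 per arm and true difference zero, power = 1 − F(t(1 − α)) with noncentrality margin/SE:

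| Assumed margin | Level | SD 1.0 | SD 1.5 | SD 2.0 |
|---|---|---|---|---|
| 0.5 | one-sided 0.05 | 91% | 64% | 44% |
| 0.75 | one-sided 0.05 | 99.8% | 91% | 73% |
| 1.0 | one-sided 0.05 | >99.9% | 99% | 91% |
| 0.5 | upper limit of two-sided 95% CI | 85% | 52% | 32% |

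At SD 2.5, the 1.0-point margin at one-sided 0.05 has 78% power. These margins only illustrate the trade-off and are not proposals.

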WISDM: **Wisconsin Inventory of Smoking Dependence Motives (Brief)**: a 37 item questionnaire to measure tobacco dependence by measuring a variety of smoking motives.

Study Synopsis

Study Design:	This single-blind, between-subject, randomized, multi-center study will assess the effect of cigarettes with unventilated vs. ventilated filters on smoking behavior and biomarkers of tobacco toxicant exposure. The study uses telehealth and brief in-clinic or curbside visits and will also examine the feasibility of remote collection of multiple biological samples. Subjective measures, alveolar carbon monoxide, blood pressure and cigarettes per day will be collected remotely. Biological samples collected at home will be dropped off at the clinic during a brief clinic or curbside visit where the study cigarettes will be dispensed.
Primary Aim:	To examine the effects of unventilated vs ventilated filter cigarettes on urinary biomarkers of toxicant exposure and smoking behavior (e.g., cigarettes per day, intensity of smoking).
Secondary Aim	To examine the effect of unventilated vs. ventilated filter cigarettes on cigarette dependence and subjective responses to cigarettes (e.g., perceptions of harm).
Exploratory Aim	To examine how the biomarkers analysis collected via different biological samples are concordant.
Population:	Cigarette smokers
Study Procedures:	Smokers using conventional cigarette brands with filter ventilation of about 16-36% will enter a three phase study. Phase 1 is a 1-week baseline period of smoking usual brand cigarettes; Phase 2 consists of 2 weeks of smoking ventilated study cigarettes; and Phase 3 where subjects are randomly assigned to one of two conditions: 1) ventilated cigarettes; or 2) unventilated cigarettes smoked for a 6 week period. Weekly telehealth visits are conducted to collect study measures and subjects attend a brief clinic or curbside visit to pick up study cigarettes and drop off biomarker samples. A follow-up telehealth visit will occur at one-month post intervention.
Accrual Goal:	162 (81 per group) enrolled
Enrollment Period	May 2021 – December 2022

1 Study Objectives and Hypotheses

The goals of this project are to determine the effects of varying degrees of cigarette filter ventilation on biomarkers of toxicant exposure and smoking behavior and on subjective responses to the cigarette.

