6.2 Biological Specimens

Biological samples will be collected and brought to the clinic or curbside visits for biomarkers analysis. Subjects will be asked to collect urine and saliva sample at weeks 92, 00, 3 and 6 visits for biomarker assessments. Buccal cells will be collected during the telehealth, in-person clinic visit or curbside at weeks 0 and 6. Blood spots (optional) will be collected at weeks 00 and 6. Hair collection will be optional and collected at week 6. These optional samples will be used to determine the feasibility of collection and analytic capabilities and concordance of results across biosample type. Participants who have experienced extensive hair loss will be exempt from the hair sample collection. The optional biosamples collected over the duration of the study will be at the discretion of the lead PI's. This would occur if it is determined that one type of biomarker has a negative impact on recruitment (e.g., few people willing to collect hair sample) or we find the sample(s) collected do not yield sufficient biomarker levels. Cigarette butts (24-hour collection) will be collected at visits 00, 3 and 6 and the butts from the inhalation measures.

Samples will be stored in a -20 or -80°C freezer. Specimens will be collected, stored at sites and shipped to the Masonic Cancer Center at intervals upon request from the lead site.

The samples may be stored until they are used up or no longer needed up to a maximum of 10 years from the study's end. A subject has the right to withdraw consent at any time by informing the Principal Investigator by following the instructions provided in the HIPAA document. If this occurs any remaining identifiable research sample(s) will be destroyed.

Rationale for choice of biomarkers:

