The biomarkers for this project have been selected to represent exposures to carcinogens. We have chosen 2 types of biomarkers found in saliva, blood spots or hair. The first is related to nicotine intake, namely total nicotine equivalents (TNE). Knowing that smokers adjust their smoking behavior to maintain nicotine exposure, it is important to understand if this occurs when smoking an unventilated cigarette (e.g., complete or partial compensation). Also, because tobacco carcinogens are increased with filter ventilation, the consideration of intake of these carcinogens are important to understand in the context of the nicotine intake. Thus, the other validated biomarker, NNAL, was selected to represent exposure to carcinogenic tobacco specific nitrosamines because this is a known lung carcinogen. DNA adducts N6-hydroxymethyl-deoxyadenosine and N2-ethylidene-deoxyguanosine derived from formaldehyde and acetaldehyde, respectively. DNA adducts will be analyzed in buccal cells. Buccal cells (cells gently scraped from the inside of the cheek with a cytobrush) can serve as a minimally invasive tool to measure the responses to tobacco and can be leveraged to determine the biological effects associated with tobacco- and nicotine-related toxicant exposure.

Biomarker Analysis:

The following biomarkers has been selected to represent exposures to nicotine and carcinogen, NNK:

- 1) Nicotine: Total nicotine equivalents – TNE (molar sum of nicotine and its metabolites) in urine will be used primarily to assess overall cigarette exposure. For subjects who state they are no longer smoking, we will confirm cigarette-free days and abstinence from all tobacco products with TNE. TNE was selected because it accounts for 73-96% of the nicotine dose and is a useful measure of daily nicotine exposure. Nicotine metabolite ratios can also provide other important information, such as differences in nicotine metabolism rate. Cotinine and 3-hydroxycotinine will be measured in saliva and blood spots for comparison across the different assays.
- 2) Biomarkers of Carcinogen Exposure have shown good laboratory reproducibility, have clear differences in levels between smokers and nonsmokers and/or decrease upon tobacco cessation, and reflect differences in toxicants in the various tobacco/nicotine products.^{30,31}

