 - a. 4-(methylnitrosamino)-1-(3-pyridyl)-1-butanol (NNAL) and its N- and O-glucuronides (exposure to tobacco-specific lung carcinogen NNK) in urine and possibly hair or blood spots.
 - b. Tobacco specific oral and esophageal carcinogen N'-nitrosonornicotine (NNN) and its N-glucuronide in urine.
 - c. Phenanthrene tetraol and 3-hydroxy phenanthrene (exposure to and metabolism of the representative polycyclic aromatic hydrocarbon phenanthrene) in urine.
 - d. Mercapturic acids (exposure to acrylonitrile (CEMA), acrolein (3-HPMA) and crotonaldehyde (HMPMA) in urine.
 - e. DNA adducts N6-hydroxymethyl-deoxyadenosine and N2-ethylidene-deoxyguanosine derived from formaldehyde and acetaldehyde, respectively. DNA adducts will be analyzed in buccal cells
- 3) Inflammatory and Oxidative Stress Biomarkers
PGE-M and 8-*iso*-PGF_{2 α} in urine will be measured to assess inflammation and oxidative stress.
- 4) Other biomarkers
 - a. Untargeted metabolomics also will be measured in the urine by gas chromatography and mass spectroscopy. This is an emerging technology that provides a broad screen for exposures and cellular responses that represent biomarkers of exposure and potential harm. They will be employed for the analysis of urine to identify novel biomarker profiles distinguishing exposures from ventilated and non-ventilated cigarettes for totality of cigarette smoke-derived exposures and endogenous cellular responses.^{32,33}
 - b. Exhaled carbon monoxide (CO) collected at every clinic visit.
 - c. In addition, other tobacco-related validated biomarkers for assessment in urine, saliva, buccal cells, hair or blood spots may be developed over time and these additional

assays will be completed as appropriate using samples stored in the Biobank. Also, in the future, samples may be analyzed for metabolism of tobacco toxicants or nicotine and tobacco-related exposures or harm.

5) Spent Filter Analysis:

Filters will be collected at Week 00, Week 3 and after 6 weeks on study cigarettes. They will be analyzed for constituent yield and filter ventilation blocking and may also be used for filter staining analysis. For extraction of spent cigarette filters, one-cm portions will be removed from the mouth end of the spent cigarette filters, stripped of the wrapping paper and transferred into clean vials for constituent extraction. Filters will be analyzed for nicotine, TSNA, and PAH. Cigarette butts will be collected the day before visit 00, 3 and 6.

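### The exploratory endpoint is concordance of biomarker levels across biosamples, but the only planned analysis is correlation, which can stay high when one sample type differs systematically from another

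*Combined protocol and SAP*

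**What the plan says.** The Study Synopsis gives the exploratory aim as "To examine how the biomarkers analysis collected via different biological samples are concordant". Section 1.2 names urine, saliva, blood spots and hair as the sample types and adds a hypothesis about level: "We also hypothesize the level of toxicant exposure will be concordant across various methods of collecting biological samples". Section 10.1 lists the exploratory endpoint as "Determine concordance in biomarkers of exposure across different sample collection methods". Section 6.2 gives concordance as one purpose of the optional blood-spot and hair samples: "These optional samples will be used to determine the feasibility of collection and analytic capabilities and concordance of results across biosample type".

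On what will be compared, section 6.2 says "Cotinine and 3-hydroxycotinine will be measured in saliva and blood spots for comparison across the different assays". NNAL is to be assayed "in urine and possibly hair or blood spots".

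The analysis is a single sentence under Exploratory Analysis in section 10.2: "Correlation procedures (Pearson and Spearman) will measure the degree of association for the same biomarkers assayed from two or more biosamples". The documents contain no agreement statistic, no calibration between sample types, no list of analyte pairs and visits, and no criterion for calling two samples concordant.

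**The concern.** The hypothesis is about the level of exposure, and the planned statistics do not measure agreement in level. Pearson's coefficient is unchanged by any positive linear rescaling of either variable, and Spearman's by any increasing transformation. Two sample types that differ twofold throughout, or one that compresses the range, can therefore give a high correlation.

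What is at stake is how the exploratory result is read. Feasibility of remote collection of several biosamples is one of the study's stated interests. A high correlation could be taken to mean that one sample type can stand in for another, when the planned analysis has not examined whether the ratio between them is stable across light and heavy smokers.

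**Working it through.** The plan states no sample size, target correlation or agreement limit for this endpoint, so there is no figure to reproduce. The check is whether the planned statistic responds to systematic disagreement.

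**Inputs, all assumed.** True between-subject SD on the natural-log scale 0.7 (variance 0.49). Assay SD 0.2 on each sample (variance 0.04). Sample A therefore has total variance 0.49 + 0.04 = 0.53.

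**Case 1: B reads k times A on average.** On the log scale this is a shift of ln k. Both variances are 0.53 and the covariance is 0.49.

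- Pearson: r = 0.49 / 0.53 = 0.92 for every k.
- Lin's coefficient: CCC = 2 × 0.49 / (0.53 + 0.53 + (ln k)²).

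| k | (ln k)² | r | CCC |
|---|---|---|---|
| 1 | 0 | 0.92 | 0.98 / 1.060 = 0.92 |
| 1.5 | 0.164 | 0.92 | 0.98 / 1.224 = 0.80 |
| 2 | 0.480 | 0.92 | 0.98 / 1.540 = 0.64 |

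**Case 2: log-log slope 0.6, same geometric mean, assay SD 0.2 on both samples.**

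- Covariance = 0.6 × 0.49 = 0.294.
- Variance of B = 0.36 × 0.49 + 0.04 = 0.2164.
- r = 0.294 / √(0.53 × 0.2164) = 0.87.
- Relative to a slope of 1, B at -1 SD is off by exp(0.4 × 0.7) = exp(0.28) = 1.32, or 32% high. At +1 SD it is off by exp(-0.28) = 0.76, or 24% low.

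**What limits of agreement would show on the same inputs.**

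- Case 1: the SD of the log difference is √(0.04 + 0.04) = 0.283, and exp(1.96 × 0.283) = 1.74. The 95% limits for the ratio B/A are 0.57 to 1.74 at k = 1, and twice that, 1.15 to 3.48, at k = 2. The offset is visible and can be judged on its merits.
- Case 2: the SD is √(0.16 × 0.49 + 0.08) = 0.398, and exp(1.96 × 0.398) = 2.18. The limits widen to 0.46 to 2.18, and the difference trends downward against the mean.

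**Sensitivity to the assumptions.** A simulation with log SD 0.8, assay SD 0.18 and 146 subjects (2 × the 73 per group in the sample-size section) gave:

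| Scenario | Pearson | Spearman | CCC |
|---|---|---|---|
| No bias | 0.95 | 0.95 | 0.95 |
| B reads 2-fold higher | 0.95 | 0.94 | 0.70 |
| B reads 3-fold higher | 0.95 | 0.94 | 0.50 |
| Slope 0.5 plus 2-fold | 0.89 | 0.88 | 0.47 |
| Added random noise, SD 0.8 | 0.68 | 0.66 | 0.64 |

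In closed form at r = 0.95 with a 2-fold ratio, CCC is 0.48, 0.69 and 0.77 for log SDs of 0.5, 0.8 and 1.0. The size of the gap depends on the assumed spread; that there is a gap does not.

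**The case against.** The strongest reply is that saliva, blood spots, urine and hair are different matrices. Nothing in the documents says their levels should be equal, so a constant ratio between them may be legitimate. The fall in Lin's coefficient in Case 1 is a penalty for exactly that offset. This stands: Lin's coefficient is not a fit summary for most of these pairs, and a slope other than 1 is not in itself an error. It does not rescue correlation as the sole analysis, because the ratio between two matrices, its scatter and its stability across levels can be examined on the log scale without assuming that levels are equal. The 3-hydroxycotinine/cotinine ratio has no units at all.

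Other limits also stand. Correlations do fall when disagreement is random, as the last simulation row shows. An errors-in-variables slope needs the ratio of assay error variances, and the documents give neither assay variances nor duplicate assays.

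A reader might infer more than the text supports:

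- That repeated visits will be pooled as if independent. Section 10.2 does not say so; correlations could be run visit by visit. Hair is collected only at week 6 and has no repeat.
- That the trial will declare home-collected samples concordant. No threshold is set, and section 10.2 itself describes what the correlations measure as association. Nor is a home-versus-clinic comparison planned: urine and saliva are both collected at home.

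**Conclusion.** The mismatch between endpoint and analysis is real and rests on the text alone: concordance of levels is the aim, hypothesis and endpoint, and correlation is the whole analysis. The statistical consequence is limited to systematic disagreement, meaning a constant ratio or a log-log slope other than 1. Under the assumed SDs, r stays at 0.92 across a twofold shift and at 0.87 with a slope of 0.6. It would be too strong to say that the correlations stay high whenever samples disagree, or that any offset between matrices is a fault.

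The point is minor. The endpoint is exploratory, the blood-spot and hair samples are optional and may be dropped at the lead investigators' discretion, and no primary or secondary analysis depends on it.

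**What to change.** Keep Pearson and Spearman as descriptive measures and add the following to section 10.2.

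1. Name the pairs and visits: saliva versus blood-spot cotinine, 3-hydroxycotinine and their ratio (both sample types are collected at visits 00 and 6), and NNAL pairs if assayed.
2. For each pair, report on the log scale the mean between-matrix ratio with 95% limits of agreement.
3. Check whether the ratio changes with level. Either plot and regress the log difference on the log mean, noting that unequal assay error can also produce a trend, or fit an errors-in-variables slope with a stated error-variance ratio and a sensitivity range.
4. Use Lin's coefficient only where the same quantity in the same units is expected, for example the 3-hydroxycotinine/cotinine ratio.
5. Analyse by visit, or include a subject random effect if visits are pooled.

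If only association is intended, restate the endpoint and hypothesis as association and draw no conclusion about concordance of levels.

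The cost is a little more analysis of samples already planned, an explicit assumption if an errors-in-variables slope is used, and possibly a less favourable statement about concordance.
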